SOVA pilot efficacy study findings show support for the underlying conceptual model, study feasibility, and improved uptake of treatment at 3 months. We conducted a pilot efficacy randomized controlled trial to compare SOVA to Enhanced Usual Care (EUC) in a single high-resource adolescent medicine clinic that provides primary and specialty care and has multiple behavioral health providers who work alongside medical providers in a team based approach. Out of 167 adolescents screened, 35 were randomized, and 24 completed follow-up measures. At baseline, adolescents with a lower perceived need for mental health treatment also had higher stigma scores (20.9 ± 10.7 vs. 18.6 ± 7.5 , $p=.48$), lower depression knowledge (10.9 ± 3.4 vs. 12.7 ± 3.2 , $p=.16$) and anxiety knowledge (6.9 ± 2.0 vs. 9.5 ± 2.9 , $p=.02$), higher barriers to seeking therapy (3.2 ± 0.8 vs. 2.6 ± 0.8 , $p=.07$) and lower social support (75.3 ± 29.2 vs. 88.5 ± 22.8 , $p=.18$). We found that at 3 months, 11/13 (85%) adolescents randomized to SOVA received mental health treatment as compared to 6/11 (55%) adolescents randomized to EUC ($p=.18$), where receipt of treatment was measured by a combination of either adolescent or parent self-report and a blinded manual electronic health record extraction. We found limited engagement in the treatment arm with only 50% of adolescents randomized to SOVA accessing the intervention, several

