citing they would forget about looking at it. When using a per protocol analysis comparing those who accessed SOVA (n=5) at least once to those who were in the EUC arm or did not access SOVA (n=17), we found a signal for some targets including a decrease in stigma76 (-3.6 ± 5.5 vs. -2.6 ± 8.1 , $p=.67$), an increase in social support (2.5 ± 23.6 vs. -0.2 ± 28.4 , $p=.64$), a decrease in attitudinal barriers toward therapy-seeking (-0.4 ± 2.4 vs. -0.2 ± 1.7 , $p=.97$) and an increase in general functioning (2.8 ± 4.7 vs. -0.8 ± 5.8 , $p=.22$). During the trial, recruitment rate increased after passing a waiver for parental permission and not requiring adolescents to enter the study as a dyad with a parent. This change is conceptually consistent as adolescents who have poor communication with their parent are a SOVA target population but may be more difficult to recruit if parental permission is required. We began to use text messages to send out links to online surveys due to low adolescent use of email. We determined that our safety protocols were adequate and experienced no adverse events.

The next step in further developing SOVA and wiseSOVA is to test it with a screening tool and follow up on a conversation where a provider makes a recommendation based on a youth or young adults mental health screening results.

Study Objectives

We propose a pilot randomized controlled trial of 100 youth who present to primary care settings or other specialty medical settings. Consenting participants will be randomized to one of three conditions in a 2:2:1 randomization scheme to either receive “Treatment as usual” which is a basic report listing mental health symptom scores (n=20), Screening Wizard 2.0, which includes symptom score report plus the enhanced screening questions and treatment guidelines (n=40), or Screening Wizard 2.0 + SOVA, a website encouraging patients to use referred mental health services (n=40). All participants will then complete a brief battery of self-report assessments at baseline and again after 12 weeks.

Aim 1. To examine the efficacy of Screening Wizard 2.0 at improving the process of screening and referral for youth with depression and/or suicidality:

Hypothesis 1: Screening Wizard 2.0 will result in more referrals to a mental health provider for symptoms of depression and/or suicidality compared to “Treatment as usual” (increase >30% compared to “Treatment as usual”)

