Hypothesis 2: Screening Wizard 2.0 will result in higher rates of follow-through with mental health services (defined as attendance at an initial appointment) compared to “Treatment as usual” (increase >30% compared to “Treatment as usual”)

Hypothesis 3: Screening Wizard 2.0 will have higher adolescent and parent perception of being involved in a shared decision-making process compared to “Treatment as usual” (SW involvement > “screening as usual” involvement)

Aim 2. To examine the added efficacy of SOVA in combination with Screening Wizard 2.0:

Hypothesis 1: Adolescent and parents in Screening Wizard 2.0 + SOVA will have less negative attitudes about psychotherapy, higher depression literacy, and a higher readiness for treatment as compared to Screening Wizard 2.0 alone or “screening as usual.”

Hypothesis 2: Adolescent and parents in Screening Wizard 2.0 + SOVA will result in higher rates of follow-through with mental health services (defined as attendance at an initial appointment) compared to Screening Wizard 2.0 alone (increase >10%) and “screening as usual” (increase >40%)

Study Design & Method

We will conduct a 3-arm randomized trial of Screening Wizard 2.0 in 100 youth (age 12-26) presenting to clinical care in primary care and community mental health settings onboarded to the study.

Arm 1 will include 20 participants randomized to receive “Treatment As Usual.” This will include the practice’s standard practice for the presenting patient which may include universal screening for depression and/or suicidality with the practice-preferred screening instrument/modality, targeted screening (decision to screen based on symptoms or complaint), and/or no screening. Due to practice heterogeneity and our pilot findings that attempting to standardize the control arm disrupted clinical workflows and recruitment rates, we will not standardize the practices’ screening instrument or practice. We will ask that the participant complete SW (via email link or over the phone) and study staff will provide a list of symptom scores to provider in this arm, regardless of type of screening processes are in place.

Arm 2 will include 40 participants who will be given the Screening Wizard 2.0 tool and the provider will be given a detailed output report of symptom scores highlighting any acute concerns such as suicidality, patient treatment preferences, and potential patient barriers to treatment.

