Arm 3 will include 40 participants who will be given the Screening Wizard 2.0 and the provider will be given the detailed output report as well as participant and parent given access to the SOVA intervention (regardless of results).

Youth randomized to receive SOVA will be asked to provide their desired usernames and will be provided with log-ins to the website intervention. Youth and parents will then be contacted for an onboarding phone call explaining use of the site, and receive weekly text messages reminding them to view articles which may be relevant to addressing specific barriers they identified using Screening Wizard as well as new articles written by other youth with lived mental health experiences (i.e. SOVA Peer Ambassadors).

Screening Wizard 2.0 Questions

The screening wizard will administer the standard of care measures (i.e. PHQ-9 depression screener and SBIRT-CRAFFT substance use questions) in addition to the supplemental questions (i.e. preferences for treatment, readiness, co-morbid dx, etc.) to complete the intervention.

If the family chooses to take the screening wizard questionnaire at a different time than before their scheduled appointment (telehealth or in person), the research staff/ARC assessors will provide the primary care provider with the Screening Wizard results, so that s/he can follow up on positive screens for depression and/or suicidality. Imminent risk will be managed through the ETUDES study safety management protocol.

Screening Wizard 2.0 Basic Report vs. Intervention Report

The Basic report is a report of symptom scores that populates from Screening Wizard 2.0 will be provided to ARM 1 participant providers and this follows current standard of care. The conditions screened include: depression, anxiety, mania, suicidality, and substance use. The overall scores and each individual response to the symptom questions are contained on this report. Based on qualitative feedback and interaction with providers in Phase 1b trial of, providing item level details as well as overall scores was necessary and preferred and process was developed to match current standard of care so it could be adopted by the practice.

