peer ambassador) and in response to each other. They can also participate in a discussion board where they can start or respond to threads and post questions and comments. Besides comments and discussion boards, users cannot interact with each other and are anonymous. New articles are posted every weekday covering topics from “How to Start a Conversation about Suicide” to “Why Do Plants Improve Our Mood” and “Instagram Invites.” Most are written with an intended youth voice by the research team graduate students in their early 20’s and about a third by SOVA Peer Ambassadors. All posts are reviewed by the research team using established tools for health literacy and readability with a goal of 8 or lower. All comments are reviewed and screened by a research team moderator (at least every 3 hours) and any comments that violate ground rules (e.g., include identifying information, bullying, imply suicidality) are removed (in prior studies, we have observed no bullying and only removed comments due to identifying information). Although no user has implied suicidality on the site in the past, moderators will follow a suicidality protocol as described in human subjects if a user posts such a comment to clarify its meaning, potential extent of suicidality, and provide support. Moderators will also encourage comments from users if no other user has responded in 24 hours by offering gratitude and encouragement, asking follow-up questions, and limiting their own opinion/experience. Parents who enroll for the site with their child will have access to the wiseSOVA site only and view blog posts there that are on parallel daily topics. Posts composed for the adolescent site are modified by the website editor for a parent audience (i.e., same topic written about with guidance for parents; SOVA ambassador’s articles featured with introduction for parents that reading an article from a young person’s perspective may help them consider their child’s viewpoint and can be used as a conversation starter). Parents will also have access to a discussion board and commenting, but there will not be parent ambassadors. Prior stakeholder feedback from parents found they lacked a desire to use the wiseSOVA site for peer blogging; they preferred to use it to access information when needed, but not longitudinally as they would then move on to prioritize other tasks. For adolescents whose parents do not enroll in the study, during the informational phone call, the RA will provide them with information about wiseSOVA that they can offer to their parent or guardian if they choose – as a goal of using SOVA is to encourage them to communicate about mental health with their parent or guardian.

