-Hypothesis 1: Screening Wizard 2.0 will result in more referrals compared to “Treatment as usual” (increase >30% compared to “Treatment as usual”). We will calculate referral rates for each condition and compare them using chi-square tests.

-Hypothesis 2: Screening Wizard 2.0 will result in higher rates of follow-through with mental health services compared to “Treatment as usual” (increase >30% compared to “Treatment as usual”) We will calculate follow-through rates for each condition and compare them using chi-square tests.

-Hypothesis 3: Screening Wizard 2.0 will have higher patient satisfaction compared to “Treatment as usual” (Screening Wizard 2.0 satisfaction > “Treatment as usual” satisfaction). We will calculate mean satisfaction scores (CSQ) scores for each condition and compare them using t-tests.

Aim 2. To examine the added efficacy of SOVA in combination with SW:

-Hypothesis 1: Adolescent and parents in Screening Wizard 2.0 + SOVA will have less negative attitudes about psychotherapy, higher depression literacy, and a higher readiness for treatment as compared to Screening Wizard 2.0 alone or “Treatment as usual.” We will calculate mean psychotherapy attitudes using the BASH-B scale for adolescents, and Parent version BASH scale; and depression literacy using the D-LIT scales and compare them using t-tests. We will collapse readiness for treatment for parents and teens to ready vs. not ready and compare these using a Chi-square test.

-Hypothesis 2: Adolescent and parents in Screening Wizard 2.0 + SOVA will result in higher rates of follow-through with mental health services (defined as attendance at an initial appointment) compared to Screening Wizard 2.0 alone (increase >10%) and “Treatment as usual” (increase >40%). We will calculate follow-through rates for each condition and compare them using chi-square tests.

Power Analysis. The proposed study is a preliminary randomized pilot study. We expect that the small sample will provide sufficient comparison data to guide the design of a larger-scale controlled study that would be sufficiently powered to determine the efficacy of the intervention.

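### Aim 2 Hypothesis 1 compares attitude and literacy scores by unadjusted t-test; adjusting for baseline would be more precise for any scale shown to be collected before allocation

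*Combined protocol and SAP*

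**What the plan says.** Under Statistical Considerations, Aim 2 Hypothesis 1, the plan states: "We will calculate mean psychotherapy attitudes using the BASH-B scale for adolescents, and Parent version BASH scale". It continues with "depression literacy using the D-LIT scales and compare them using t-tests". The text names no covariate, does not mention change scores, and does not say at which visit the means are taken.

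Study Objectives gives the assessment times: "All participants will then complete a brief battery of self-report assessments at baseline and again after 12 weeks". The instruments in the battery are not listed. The paragraph describes allocation before it describes the battery: "Consenting participants will be randomized to one of three conditions in a 2:2:1 randomization scheme".

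Study Design & Method sets the arm sizes at 20 for treatment as usual (TAU), 40 for Screening Wizard (SW) and 40 for SW + SOVA. The Power Analysis paragraph claims no power. It gives the purpose as supplying comparison data for designing a larger trial.

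**The concern.** When a scale is measured at baseline and again at follow-up, the baseline score usually predicts the follow-up score. A two-sample t-test on the follow-up scores ignores that and leaves explainable variation in the error term. Adjusting for a baseline taken before allocation removes it and does not disturb the randomised comparison.

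Precision is what this pilot has to offer the larger trial, and there is little of it. The TAU arm has 20 youth, the earlier SOVA pilot lost about a third of its participants, and the SOVA Intervention section allows for parents who do not take part. Wider intervals than necessary on the arm differences make the pilot less useful for planning.

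**Working it through.** **Inputs from the documents.** The arm sizes are 20, 40 and 40 ("Arm 1 will include 20 participants randomized to receive"; "Arm 3 will include 40 participants who will be given the Screening Wizard 2.0"), which agrees with 100 split 2:2:1. The plan has no power figure to reproduce. For retention I use the earlier pilot as a sensitivity case ("35 were randomized, and 24 completed follow-up measures"): 24/35 = 0.686, so 40 becomes 27 and 20 becomes 14.

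**Assumptions, because the documents give no figure.** True difference d = 0.5 SD; two-sided 5%; baseline-to-12-week correlation r = 0, 0.3, 0.5 or 0.7; half of parents enrolling.

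**Formulas** (noncentral t, SD = 1, N = n1 + n2):
- t-test on 12-week scores: SE = √(1/n1 + 1/n2), df = N − 2.
- ANCOVA: SE = √[(1/n1 + 1/n2)(1 − r²)(1 + 1/(N − 4))], df = N − 3. The last factor is the cost of estimating the slope.
- t-test on change scores: SE = √[(1/n1 + 1/n2) × 2(1 − r)], df = N − 2.

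**Worked case, 40 v 40, r = 0.5.** The t-test SE is √(1/40 + 1/40) = 0.2236. The ANCOVA SE is 0.2236 × √(0.75 × (1 + 1/76)) = 0.1949. The noncentrality is 0.5/0.1949 = 2.565 and the critical value on 77 df is 1.991, so power is 71.7%, against 59.8% for the t-test. The 95% CI half-width falls from 0.445 to 1.991 × 0.1949 = 0.388 SD.

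**Power, %** (gains taken before rounding):

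| Scenario | n | t-test | ANCOVA r = 0 | 0.3 | 0.5 | 0.7 | Gain at 0.5, points |
|---|---|---|---|---|---|---|---|
| Full, SW+SOVA v SW | 40 v 40 | 59.8 | 59.2 | 63.3 | 71.7 | 86.7 | 11.9 |
| Full, SW+SOVA v TAU | 20 v 40 | 43.5 | 42.8 | 46.2 | 53.8 | 70.2 | 10.3 |
| 69% retained | 27 v 27 | 43.8 | 43.1 | 46.5 | 54.0 | 70.5 | 10.2 |
| 69% retained | 14 v 27 | 31.6 | 30.9 | 33.4 | 39.2 | 53.4 | 7.6 |
| Half of parents | 20 v 20 | 33.8 | 33.0 | 35.7 | 41.9 | 56.6 | 8.1 |
| Half of parents | 10 v 20 | 23.9 | 23.1 | 24.9 | 29.2 | 40.2 | 5.3 |
| Half of parents, 69% retained | 14 v 14 | 24.7 | 23.9 | 25.7 | 30.2 | 41.5 | 5.5 |
| Half of parents, 69% retained | 7 v 14 | 17.7 | 16.9 | 18.1 | 20.9 | 28.5 | 3.3 |

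At r = 0 the loss is under 1 point in every row. ANCOVA overtakes the t-test once r exceeds about 0.12 (40 v 40) or 0.13 (20 v 40), rising to 0.20 at 10 v 20. For 20 v 40 the CI half-width is 0.548 SD by t-test and 0.479 SD by ANCOVA at r = 0.5.

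**If change scores were intended.** At 40 v 40 the change-score t-test has power 46%, 60% and 81% at r = 0.3, 0.5 and 0.7, against 63%, 72% and 87% for ANCOVA. ANCOVA is still ahead, but by a different amount.

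**What the documents suggest about r.** With equal SDs at both times, r = 1 − SD(change)²/(2 × SD(baseline)²). The earlier pilot's stigma SDs (baseline 10.7 and 7.5; change 5.5 and 8.1) give between 1 − 8.1²/(2 × 7.5²) = 0.42 and 1 − 5.5²/(2 × 10.7²) = 0.87. I place little weight on this: the groups are small and defined differently at the two steps, and stigma is not one of the scales at issue. The same method applied to the barriers scale (0.8 and 2.4) gives 1 − 2.4²/(2 × 0.8²) = −3.5, which is impossible.

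**The case against.** The strongest objection is to the premise. A reader might infer that the team holds a pre-allocation baseline score for each scale and discards it. The documents do not support that. They never say that BASH-B, parent BASH or D-LIT is in the battery, and the literal order in Study Objectives puts the battery after randomisation. If baseline were completed after the participant knew the arm or had SOVA access, it could be affected by allocation, and adjusting for it could introduce bias. This stands, and it is why the recommendation is conditional. The opposite inference, that baseline definitely follows allocation, is not established either: the wording is a loose summary, not a visit schedule.

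For parents the premise is weaker. The sentence on the battery follows a description of 100 youth, no passage expressly gives parents a baseline assessment, and the SOVA Intervention section makes provision "For adolescents whose parents do not enroll in the study". This also stands.

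The test might also be meant for change scores, since the earlier pilot's targets were reported as changes. Baseline would then already be used. This affects the size of the gain; ANCOVA still has the higher power at each correlation checked.

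Finally, this is a preliminary pilot with no power claim, and unadjusted comparisons would still give it SDs, retention and arm differences. That is correct and limits the importance of the point.

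**Conclusion.** The point holds as a conditional gain in precision. A reader might conclude that the planned t-test is invalid or biased; it is neither, because an unadjusted comparison of randomised arms at 12 weeks is sound. No stated power figure or conclusion is overturned.

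At an assumed correlation of 0.5 and a 0.5 SD effect, the gain over a 12-week t-test is about 10 to 12 points of power at full youth enrolment, 8 to 10 at 69% retention, and 3 to 8 for parent scales at half enrolment, with or without that loss to follow-up. At 0.3 it is at most about 4 points. The size rests on a correlation, an effect size and a parent enrolment rate that the documents do not give. Whether the gain is available at all depends on each scale being in the baseline battery and completed before allocation. The improvement is worth making because it costs little; its importance is modest.

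**What to change.** 1. State which of BASH-B, parent BASH and D-LIT are in the baseline battery, whether parents complete one, and whether it is completed before allocation is assigned or disclosed.
2. Name the 12-week score as the outcome for Aim 2 Hypothesis 1.
3. For each scale that meets both conditions, replace the t-test with ANCOVA of the 12-week score on arm and the participant's own baseline score, fitted separately for youth and parents. Report the adjusted SW + SOVA v SW and SW + SOVA v TAU differences with 95% CIs.
4. Replace a missing baseline by the overall mean across arms, so that nobody with a 12-week score is dropped.
5. For any scale not collected before allocation, keep the unadjusted 12-week comparison.

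If the scales are already collected before allocation, the cost is a change of SAP wording, one degree of freedom and the missing-baseline rule. If they are not, the gain requires a longer baseline questionnaire or moving it ahead of allocation, and the team should decide whether that is worthwhile, particularly for parents.

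### Readiness for treatment is cut to ready/not ready and compared by chi-square, which discards information in arms of 20 to 40; it should be analysed on its ordered scale, separately for youth and parents

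*Combined protocol and SAP*

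**What the plan says.** Statistical Considerations, Aim 2, Hypothesis 1 sets the rule for readiness: "We will collapse readiness for treatment for parents and teens to ready vs. not ready and compare these using a Chi-square test". The hypothesis is that youth and parents given SOVA will show "higher readiness for treatment as compared to Screening Wizard 2.0 alone or" treatment as usual, so there are two arm contrasts. By Study Objectives the arms are 40 (Screening Wizard plus SOVA), 40 (Screening Wizard alone) and 20 (treatment as usual).

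The other two outcomes in the same hypothesis keep their scores. For attitudes the plan says "We will calculate mean psychotherapy attitudes using the BASH-B scale for adolescents, and Parent version BASH scale"; depression literacy is likewise scored, and both are compared by t-tests. Only readiness is cut to two categories.

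The document does not name the readiness measure, its number of levels, the cut-point or the time point analysed. It does not say whether the raters are tested separately or together. Under Screening Wizard 2.0 Questions, readiness appears among the items that the tool asks "in addition to the supplemental questions (i.e. preferences for treatment, readiness, co-morbid dx, etc".

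**The concern.** Collapsing an ordered measure treats people just above and just below the cut as fully different, and everyone on the same side as identical. In arms this small, that makes a real effect of SOVA on readiness easier to miss and the estimate carried into the next trial less precise. With no cut-point stated, the split could also be chosen after the data are seen.

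A second, separate matter is that one sentence covers parents and teens together. A parent falls in the youth's arm; in the SOVA arm the plan describes "as well as participant and parent given access to the SOVA intervention". If both members' answers entered one ordinary chi-square test, positively correlated records would be counted as independent and false positives would rise. The two effects run in opposite directions: the first raises false negatives and is planned; the second raises false positives and is only possible.

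**Working it through.** **Inputs from the plan.** "Consenting participants will be randomized to one of three conditions in a 2:2:1 randomization scheme", with 100 youth: 100 × 1/5 = 20 and 100 × 2/5 = 40, which matches the stated arms. The contrasts for readiness are therefore 40 vs 40 and 20 vs 40. The plan gives no alpha, effect size or power for readiness, so there is no figure to reproduce.

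**Assumptions.** Two-sided 5%; a normal latent readiness score; three or five equal-probability levels; shifts of 0.65 and 0.3 SD; within-dyad correlation ρ of 0.3 to 0.7; a share f of youths with an enrolled parent of 0.5 or 1. None of these is in the document.

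**Step 1: information kept by a cut.** Relative to a comparison of means on a normal score, a cut at proportion p keeps φ(z_p)² / [p(1−p)].
- p = 0.5: 0.399² / 0.25 = 0.64
- p = 0.3: 0.58
- p = 0.2: 0.280² / 0.16 = 0.49
- p = 0.1: 0.34

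For a 0.5 SD difference at 80% power, the number per arm rises from 63 (means) to 102–115 (binary, with 50% down to 20% of the comparator ready).

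**Step 2: power with an ordered scale.** Simulation of the latent score cut into levels, comparing a rank-sum test with an uncorrected chi-square test at every possible cut, 0.65 SD shift:

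| Contrast | Rank test (3 or 5 levels) | Ready/not ready (range over cuts) |
|---|---|---|
| 40 vs 40 | about 72–77% | about 44–66% |
| 20 vs 40 | about 54–60% | about 33–48% |

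At 40 vs 40 the detail is 77% against 44–65% with five levels, and 72% against 54–66% with three. At 0.3 SD and 40 vs 40, the loss is about 3–9 points. Repeat runs move these figures by a point or two. The binary version had lower power at every cut and shift tried; the size of the loss depends on the scale and the cut.

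**Step 3: false-positive rate, only if raters are pooled.** With both members of a dyad in one arm, the design effect is DE = 1 + ρ × 2f/(1+f), and the actual error is 2[1 − Φ(1.96/√DE)].

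| f | ρ | DE | Actual error |
|---|---|---|---|
| 1 | 0.3 | 1.30 | 8.6% |
| 1 | 0.5 | 1.50 | 11.0% |
| 1 | 0.7 | 1.70 | 13.3% |
| 0.5 | 0.3 | 1.20 | 7.4% |
| 0.5 | 0.5 | 1.33 | 9.0% |
| 0.5 | 0.7 | 1.47 | 10.6% |

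Simulation of the pooled test at 40 vs 40 with all youths in dyads gave 8.3%, 10.5% and 13.0%, in line with the formula. If each rater is tested separately, each family gives one record per test and the error from this source stays at about 5%.

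**The case against.** **The trial is a pilot.** The Power Analysis paragraph claims no power, and readiness is one of three components of one Aim 2 hypothesis. No stated sample size or power figure changes. A ready/not-ready percentage is also easy to read. All of this stands, and it limits the weight of the point. But the same paragraph wants the data to inform a larger trial, and using the full scale serves that at almost no cost. The percentage can still be reported.

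**The loss rests on an unseen scale.** This also stands. It is why a range is given, and the low end is modest: about 6 points for a three-level scale split at the top category (72% vs 66%, 0.65 SD), or a few points when the shift is 0.3 SD.

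**A reader might infer that parents and teens go into one chi-square test.** The sentence names both and uses the singular, whereas for follow-through the plan says "We will calculate follow-through rates for each condition and compare them using chi-square tests". The document does not support treating this as settled. The preceding sentence names separate adolescent and parent attitude scales, which suggests rater-by-rater analysis. The singular also has to cover two arm contrasts, so it may name the method and not count the tests. Nor can 9–13% be taken as the general figure even under pooling, since the SOVA Intervention section provides for adolescents whose parents are not enrolled.

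**A reader might infer that baseline readiness is available and ignored.** The list of Screening Wizard items does not say that parents answer the readiness item or that it is the outcome measure. Baseline adjustment can be asked for only where the same measure is collected.

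**Conclusion.** The point holds as a choice of analysis. The plan states a rule, to dichotomise readiness and use chi-square, and an ordered-scale method uses the same data better. Under the assumptions listed, the cost at 0.65 SD is about 6 to 33 percentage points of power at 40 vs 40 (72 − 66 with three levels at the best cut; 77 − 44 with five levels at the worst). Only the direction can be given without knowing the scale.

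The within-family issue is an ambiguity, not an established error. It becomes an inflated error rate only if the raters are pooled without adjustment. The change is worth making, but it affects a secondary component of a pilot and does not call the design into question.

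**What to change.** Amend Statistical Considerations, Aim 2, Hypothesis 1 as follows:

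- Name the readiness measure, its levels and the time point analysed.
- Analyse it on its original ordered scale, separately for youth and for parents, with a proportional-odds model or a Wilcoxon rank-sum test.
- Do this for each of the two contrasts: Screening Wizard plus SOVA against Screening Wizard alone, and against treatment as usual.
- Where the same measure is collected at baseline, use the proportional-odds model with baseline readiness as a covariate.
- Report ready/not ready as a descriptive percentage by arm, with the cut fixed in advance.
- If the raters are ever combined, use a model with family as the cluster (GEE or mixed model).

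The cost is a few lines of wording and one standard model per rater, with no extra participants; baseline adjustment is asked for only where the data are already collected. The small downside is that an odds ratio or rank result is less simple to explain than a percentage, which the descriptive table still supplies.
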